# 4.5.5.6. Hypersensitivity Reactions

Two main analyses are performed in support of assessment of potential immediate hypersensitivity, including anaphylaxis as well as potential nonimmediate hypersensitivity.

**Time Period A**, of potential immediate hypersensitivity includes all TEAEs occurring from start of study drug administration up to 24 hours after end of study drug administration. For events without the hypersensitivity electronic case report form (eCRF), only date (no time) information is collected; if such event occurred on the same date as the study drug injection date, they will be included in Time Period A.

**Time Period B**, of potential non-immediate hypersensitivity, includes all TEAEs occurring more than 24 hours after the end of study drug administration, but prior to subsequent drug administration.

The counts and percentages of participants who experienced a hypersensitivity TEAE will be summarized by PT with decreasing frequency by treatment.

Analyses for both time periods are based on the following:

- Narrow and algorithm terms in Anaphylactic reaction SMQ (20000021)
- Narrow terms in Angioedema SMQ (20000024)
- Narrow terms in Severe cutaneous adverse reactions SMQ (20000020)
- Narrow terms in Hypersensitivity SMQ (20000214)
- Narrow terms in Vasculitis SMQ (20000174)

For the Anaphylactic reaction SMQ, each term is classified by scope (Narrow, Broad) and by category (A, B, C, D). All Narrow terms are category A, and all Broad terms are category B, C, or D. In addition to the usual Narrow and Broad searches, the SMQ defines an algorithm to further refine the cases of interest. For the analysis of the time period A, the Anaphylactic reaction SMQ algorithm will be included. The algorithm is based upon events that occur within Time Period A. The counts and percentages of participants who experienced a TEAE for the following will be analyzed for each of the 2 time periods:

- Any narrow term from any one of the 5 SMQs indicated above (i.e., combined search across narrow of all 5 SMQs)
- Any narrow term within each SMQ, separately (i.e., narrow SMQ search). Within query, individual PTs that satisfied the queries will be summarized. Also, a single event may satisfy multiple SMQ, in which case the event contributes to every applicable SMQ.

## 4.5.5.6.1. Severe/Serious Hypersensitivity Reactions

The severe/serious cases of treatment-emergent hypersensitivity will be considered as AESIs. A summary with severe/serious hypersensitivity reactions may be provided, if deemed necessary.

#### 4.5.5.7. Injection Site Reaction

Injection site reactions, incidence and rates, and related information reported via the "Injection Site Reactions" eCRF will be summarized by treatment. Information to be summarized includes the location of the reaction, timing of the reaction relative to study drug administration, and characteristics of the injection site reaction: erythema, induration, pain, pruritis, and edema.

Patient-based analysis and event-based analysis may be provided if necessary. The patient-based analysis summarizes all ISR questionnaire forms for an individual participant with a single statistic, typically an extreme value. This analysis allows each participant to contribute only once for each parameter, at the expense of a focus on the most extreme events. By contrast, the event-based analysis summarizes all ISR questionnaire forms received, without regard to individual participants. This provides characteristics of ISR events as a proportion of all events for which questionnaire responses were provided, at the expense of some potential bias due to differential contribution of individual participants to the analysis.

The counts and percentages of participants with treatment-emergent ISR will be summarized by treatment using the MedDRA PTs. Detailed searching criteria can be found in Appendix 6 (Section 6.6).

The PT will be listed for summary in decreasing order of incidence for tirzepatide-treated participants.

#### 4.5.5.7.1. Severe/Serious Injection Site Reactions

The severe/serious treatment-emergent injection site reactions based on TEAE searching criteria specified in Appendix 6 (Section 6.6) will be considered as AESI.

The counts and percentage of participants with severe/serious treatment-emergent ISRs will be summarized by treatment.

#### 4.5.5.8. Major Adverse Cardiovascular Events

The following positively adjudicated MACE will be considered as AESIs:

- death due to cardiovascular AEs
- myocardial infarction,
- hospitalization for unstable angina,
- hospitalization for heart failure,
- coronary interventions (such as coronary artery bypass graft or percutaneous coronary intervention), and
- cerebrovascular events, including cerebrovascular accident (stroke) and transient ischemic attack.

The counts and percentages of participants with positively adjudicated MACE may be summarized by treatment.

In addition, MACE reported by investigator may also be summarized although a MACE reported by investigator and not positively adjudicated is not considered as AESI.

A listing of participants reporting MACE events, either reported by investigator or identified by the CEC will be provided.

# 4.5.5.9. Major Depressive Disorder/Suicidal Ideation or Behavior

The severe/serious treatment-emergent major depressive disorder/suicidal ideation or behavior will be captured as AESI. Adverse events will be searched using MedDRA PT terms. Detailed searching criteria can be found in Appendix 6 (Section 6.6).

The counts and percentages of participants with TEAEs will be summarized by treatment group using MedDRA PT nested within SMQ. Events will be ordered by decreasing frequency nested within SMQ.

In addition to spontaneously reported AEs assessed by the investigator, suicidal ideation and behavior, and depression will be assessed through the use of the Columbia-Suicide Severity Rating Scale (C-SSRS) and the Patient Health Questionnaire (PHQ-9), respectively.

# 4.5.5.9.1. Patient Health Questionnaire (PHQ-9)

Total scores for the PHQ-9 range from 0 to 27 with total scores categorized as:

- None (not depressed): 0-4;
- Mild: 5 9;
- Moderate: 10 14;
- Moderately Severe: 15 19; and
- Severe: 20 27.

Shift tables will be provided showing the counts and percentages of participants within each baseline category (maximum value) versus each postbaseline category (maximum value) by treatment.

Additionally, the following 3 outcomes of interest will be compared between treatments (based on the maximum value during baseline and postbaseline):

- Any increase in depression category (i.e., worsening of depression); includes participants in the none, mild, moderate, or moderately severe category during baseline and with at least 1 postbaseline measurement;
- Increase from No or Mild Depression to Moderate, Moderately Severe or Severe Depression; includes participants in the none or mild depression category during baseline and with at least 1 postbaseline measurement; and
- Increase from Mild or Moderate Depression to Moderately Severe or Severe Depression; includes participants in the mild or moderate depression category during baseline and with at least 1 postbaseline measurement.

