- 11. Have a history of significant active or unstable major depressive disorder or other severe psychiatric disorder (for example, schizophrenia, bipolar disorder, or other serious mood or anxiety disorder) within the last 2 years

Note: Participants with major depressive disorder or generalized anxiety disorder whose disease state is considered stable for the past 2 years and expected to remain stable throughout the course of the study, in the opinion of the investigator, may be considered for inclusion if they are not on excluded medications

- 12. Have any lifetime history of a suicide attempt
- 13. Have a Patient Health Questionnaire-9 (PHQ-9) score of 15 or more at Visit 1 or 3, prior to randomization
- 14. On the Columbia-Suicide Severity Rating Scale (C-SSRS) at Visits 1 or 3, prior to randomization:
 - a. a "yes" answer to either Question 4 (Active Suicidal Ideation with Some Intent to Act, Without Specific Plan)

or

b. a "yes" answer to Question 5 (Active Suicidal Ideation with Specific Plan and Intent) on the "Suicidal Ideation" portion of the C-SSRS

c. a "yes" answer to any of the suicide-related behaviors (Actual Attempt, Interrupted Attempt, Aborted Attempt, Preparatory Act or Behavior) on the "Suicidal Behavior" portion of the C-SSRS

and

- d. the ideation or behavior occurred within the past month
- 15. Have any of the following cardiovascular conditions within 3 months prior to randomization:
 - · acute myocardial infarction
 - cerebrovascular accident (stroke)
 - · unstable angina
 - · hospitalization due to congestive heart failure
 - · uncontrolled hypertension (systolic blood pressure above or equal to 160 mmHg and/or diastolic blood pressure above or equal to 100 mmHg)
- 16. Have New York Heart Association Functional Classification IV congestive heart failure
- 17. Have a serum calcitonin level (at Visit 1) of 35 ng/L or more, as determined by central laboratory at Visit 1

- 18. Have a family or personal history of medullary thyroid carcinoma or Multiple Endocrine Neoplasia Syndrome type 2
- 19. Have a history of an active or untreated malignancy or are in remission from a clinically significant malignancy (other than basal- or squamous-cell skin cancer, in situ carcinomas of the cervix, or in situ prostate cancer) for less than 5 years
- 20. Have any other condition not listed in this section (for example, hypersensitivity or intolerance) that is a contraindication to GLP-1R agonists

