7.1. Discontinuation of Study Intervention

In rare instances, it may be necessary for a participant to permanently discontinue (definitive discontinuation) study intervention. If study intervention is definitively discontinued, the participant will remain in the study to be evaluated for all planned efficacy and safety measurements. See the Schedule of Activities for data to be collected at the time of discontinuation of study intervention and follow-up and for any further evaluations that need to be completed.

Possible reasons leading to permanent discontinuation of IP:

• participant decision

o the participant requests to discontinue IP

• clinical considerations

- o initiation of GLP-1R agonist or DPP-4 inhibitor, if participants will not or cannot discontinue them
- o intolerable GI symptoms despite management as described in Section 10.8
 - *Note:* If intolerable GI symptoms persist despite symptomatic treatment, temporary drug interruption, and resumption at a lower dose of study intervention, the participant should be discontinued from the study intervention.
- o BMI ≤18.5 kg/m² with clinically significant health condition is reached at any time during the treatment period

Note: The investigator should contact the sponsor CRP and/or CRS to discuss whether it is medically appropriate for the participant to continue study treatment.

- o diagnosis of type 1 diabetes mellitus
- o diagnosis of medullary thyroid cancer after randomization
- o significant elevation of calcitonin (Section 10.4.7.3)
- o diagnosis of acute or chronic pancreatitis
- diagnosis of an active or untreated malignancy (other than basal or squamous cell skin cancer, in situ carcinomas of the cervix, or in situ prostate cancer) after randomization
- o development of any significant study intervention-related hypersensitivity reaction
- o onset of pregnancy in a female participant
- occurrence of any other treatment-emergent adverse event (TEAE), SAE, or clinically significant finding for which the investigator believes that permanent study intervention discontinuation is the appropriate measure to be taken
- o inadvertent enrollment if continued treatment with study intervention would not be medically appropriate (Section 7.2.1)
- o PHQ-9 score ≥15

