10.4.7.12. Depression, Suicidal Ideation, or Behavior Monitoring

Participants will be monitored for depression and suicidal ideation or behavior through AE collection and by using the C-SSRS and the PHQ-9. Participants will be referred to a mental health professional if, in the opinion of the investigator, it is necessary for the safety of the participant, or if the participant had any of the following:

- a PHQ-9 score ≥15
- C-SSRS responses of
 - o A "yes" answer to either Question 4 (Active Suicidal Ideation with Some Intent to Act, Without Specific Plan)

or

o A "yes" answer to Question 5 (Active Suicidal Ideation with Specific Plan and Intent) on the "Suicidal Ideation" portion of the C-SSRS

or

 A "yes" answer to any of the suicide-related behaviors (actual attempt, interrupted attempt, aborted attempt, preparatory act, or behavior) on the "Suicidal Behavior" portion of the C-SSRS.

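### The only listed PHQ-9 comparison targeting exactly 15 or above omits participants in the lowest baseline category, although they too can cross that score

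*SAP*

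**What the plan says.** SAP section 4.5.5.9.1 bands the PHQ-9 total score into five categories. The lowest is "None (not depressed): 0-4", followed by mild (5-9), moderate (10-14), moderately severe (15-19) and severe (20-27). Baseline and post-baseline categories are both taken from the maximum score in the period. The section plans shift tables by treatment and then names three outcomes to be compared between treatments:

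1. Any rise in category. This "includes participants in the none, mild, moderate, or moderately severe category during baseline and with at least 1 postbaseline measurement".
2. "Increase from No or Mild Depression to Moderate, Moderately Severe or Severe Depression; includes participants in the none or mild depression category during baseline".
3. "Increase from Mild or Moderate Depression to Moderately Severe or Severe Depression; includes participants in the mild or moderate depression category during baseline".

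All three also require at least one post-baseline score.

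The protocol gives the score of 15 three roles:

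- Exclusion criterion 13 in section 5.2: "Have a Patient Health Questionnaire-9 (PHQ-9) score of 15 or more at Visit 1 or 3, prior to randomization".
- Section 10.4.7.12 requires referral to a mental health professional for "a PHQ-9 score ≥15".
- Section 7.1 includes "PHQ-9 score ≥15" among the possible reasons for permanently stopping study intervention, with a mental health professional helping to decide.

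**The concern.** Moderately severe or severe means 15 or more, so the third outcome is the one that lines up with the protocol's own action threshold. A comparison of who crosses a threshold should include everyone who starts below it. The third outcome leaves out those who start furthest below it.

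It also departs from the pattern of the other two. Outcome 1 admits every category from which a rise is possible. Outcome 2, whose target is moderate or worse, admits both categories below that target. Outcome 3 alone skips a category below its target, and the SAP gives no reason.

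At stake is how the result reads. A reader could take an unremarkable third comparison to mean that the arms do not differ in reaching 15 or more, when every case arising from a baseline score of 0-4 had been left out of it.

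**Working it through.** The documents give no sample size, power or expected event rate for the PHQ-9 outcomes, so there is no planned figure to reproduce. The check has three parts.

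**Which shifts each outcome counts.** Exclusion 13 applies at Visits 1 and 3, the two pre-treatment PHQ-9 assessments in the Schedule of Activities. An eligible participant's baseline category is therefore none, mild or moderate. The smallest rise is the lower bound of the target band minus the upper bound of the baseline band; the largest is the upper bound of the target band minus the lower bound of the baseline band.

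| Shift | Rise in points | Reaches 15? | Outcome 1 | Outcome 2 | Outcome 3 |
|---|---|---|---|---|---|
| None to mild | 1-9 | no | yes | no | no |
| None to moderate | 6-14 | no | yes | yes | no |
| None to moderately severe | 11-19 | yes | yes | yes | **no** |
| None to severe | 16-27 | yes | yes | yes | **no** |
| Mild to moderate | 1-9 | no | yes | yes | no |
| Mild to moderately severe | 6-14 | yes | yes | yes | yes |
| Mild to severe | 11-22 | yes | yes | yes | yes |
| Moderate to moderately severe | 1-9 | yes | yes | no | yes |
| Moderate to severe | 6-17 | yes | yes | no | yes |

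Six shifts reach 15 and outcome 3 counts four of them. The two it omits have the largest minimum rise into each target category: 11 points to moderately severe and 16 to severe. Outcomes 1 and 2 count those two shifts but mix them with shifts that stay below 15 (three in outcome 1, two in outcome 2). Outcome 2 also has no participants who were moderate at baseline. No listed outcome isolates 15 or more across the whole group at risk.

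**Size of the group compared.** SAP section 5 gives about 87 participants per arm. The documents give no baseline PHQ-9 distribution, so the share starting in the lowest category is an assumption, taken as 50% to 90%. Denominator per arm = 87 × (1 − share):

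- 50%: 87 × 0.5 = 43.5, about 44
- 60%: 87 × 0.4 = 34.8, about 35
- 70%: 87 × 0.3 = 26.1, about 26
- 80%: 87 × 0.2 = 17.4, about 17
- 90%: 87 × 0.1 = 8.7, about 9

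With all three baseline categories included, the denominator is every eligible participant with a post-baseline score, up to about 87 per arm.

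**What the restriction does to the test.** SAP section 4.5 makes Fisher's exact test the default for categorical safety responses. Take one tirzepatide arm against placebo, equal arm sizes and no events on placebo. The fewest tirzepatide events giving two-sided p < 0.05 are:

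- 87 per arm: 6 (6/87 = 6.9%); 5 against 0 gives p ≈ 0.059 and 6 against 0 gives p ≈ 0.029
- 44 per arm: 6 (6/44 = 13.6%)
- 26 per arm: 6 (6/26 = 23.1%)
- 17 per arm: 5 (5/17 = 29.4%)
- 9 per arm: 5 (5/9 = 55.6%)

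The number of events needed hardly changes as the group shrinks. The restriction removes possible events from the count without materially lowering the number required.

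**The case against.** The strongest reply is that nothing is lost. A participant going from none to severe is counted in outcome 1, in outcome 2 and in the shift table by treatment, where adding two cells gives the missing number. That stands, and it limits the point to one absent comparison.

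Other routes also exist. Severe or serious depression and suicidality events are of special interest under SAP section 4.5.5.9, C-SSRS results are summarised by arm, and the protocol's referral rule applies whatever the baseline score. This also stands: a reader might infer that participants' safety depends on this comparison, and it does not.

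It can be said that the shift table is itself compared between arms, because the Fisher default in SAP section 4.5 is not switched off for PHQ-9. That is arguable. SAP section 4.5.3.6 states such a test explicitly for laboratory shifts, whereas section 4.5.5.9.1 does not. The documents therefore do not support a flat claim that the shift table involves no comparison. Even so, a test of the whole distribution is not a test of reaching 15.

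Events at 15 or more may be few, so the assessment may rest on counts anyway. That is fair, but it favours using the full group at risk.

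Finally, the three outcomes may be meant as overlapping severity steps, with outcome 2 likewise omitting those moderate at baseline. The parallel fails: those participants are already at outcome 2's target, whereas participants in the none category are below outcome 3's.

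**Conclusion.** The gap is real and narrow. The only listed comparison whose target is exactly 15 or more leaves out one of the three baseline categories from which an eligible participant can reach it, and with it two of the six relevant shifts. This follows from the definitions alone and needs no assumption beyond exclusion 13 being applied.

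The number of participants affected is not known. The range of about 9 to 44 of 87 per arm rests on an assumed 50-90% in the lowest category and on every participant having a post-baseline score.

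Two stronger readings are tempting and should be resisted:

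- **That the comparison is confined to a symptomatic minority.** No baseline distribution is given. Excluding scores of 15 or more and unstable psychiatric disease points towards low scores. Protocol section 8.2.5 points the other way by noting a raised risk of depression in this population, and taking the maximum of two baseline scores can only move participants upward.
- **That the omitted cases are always the sharpest deteriorations.** This holds by categories crossed to a given target and by minimum rise. It does not hold for every rise in points: mild to severe can be as much as 22, while none to moderately severe can be as little as 11.

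The documents also do not support saying that new-onset severe depression goes uncollected or unreported. The change is worth making because it alters what this comparison can show at almost no cost.

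**What to change.** In SAP section 4.5.5.9.1, add a compared outcome: a rise to moderately severe or severe among participants whose baseline maximum falls in the none, mild or moderate category and who have at least one post-baseline score. Analyse it with the default Fisher's exact test. Redefining the third outcome in these terms would also work; adding a fourth has the advantage of keeping the existing contrast.

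The cost is one sentence in the SAP. No new data are needed, and neither study conduct nor the protocol's thresholds change. The downside of adding an outcome is one more descriptive safety comparison, probably with few events, so the counts should be shown beside the test result.

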## 4.5.5.9.2. Suicidal Ideation and Behavior Solicited Through C-SSRS

Suicide-related thoughts and behaviors occurring during the entire study period, based on the C-SSRS, will be summarized by treatment group. In particular, for each of the following suicide-related events, the counts and percentages of participants with the event will be summarized by treatment group:

- Died by suicide,
- Nonfatal suicide attempt,
- Interrupted attempt,
- Aborted attempt,
- Preparatory acts or behavior,
- Active suicidal ideation with specific plan and intent,
- Active suicidal ideation with some intent to act without specific plan,
- Active suicidal ideation with any methods (no plan) without intent to act,
- Nonspecific active suicidal thoughts,
- Wish to be dead, and
- Non-suicidal, self-injurious behavior.

In addition, the counts and percentages of participants who experienced at least 1 of the composite measures will be presented. The participants with at least 1 postbaseline C-SSRS assessment are included. The composite measure is determined at each assessment by the "yes" or "no" responses in the following C-SSRS categories by the study participant:

- Category 1 Wish to be Dead;
- Category 2 Non-specific Active Suicidal Thoughts;
- Category 3 Active Suicidal Ideation with Any Methods (Not Plan) without Intent to Act;
- Category 4 Active Suicidal Ideation with Some Intent to Act, without Specific Plan;
- Category 5 Active Suicidal Ideation with Specific Plan and Intent;
- Category 6 Preparatory Acts or Behavior;
- Category 7 Aborted Attempt;
- Category 8 Interrupted Attempt;
- Category 9 Actual Attempt (non-fatal);
- Category 10 Completed Suicide.

Composite endpoints of suicidal ideation and suicidal behavior based on the above categories are defined below:

- Suicidal ideation: A "yes" answer at any time during study to any 1 of the 5 suicidal ideation questions (Categories 1-5) on the C-SSRS;
- Suicidal behavior: A "yes" answer at any time during study to any 1 of the 5 suicidal behavior questions (Categories 6-10) on the C-SSRS;
- Suicidal ideation or behavior: A "yes" answer at any time during study to any 1 of the 10 suicidal ideation and behavior questions (Categories 1-10) on the C-SSRS.

A listing containing data for each participant with suicidal ideation, suicidal behavior, or non-suicidal self-injurious behavior during the study may be provided. Data from all visits are displayed, regardless of a "yes" or "no" answer, for participants with any "yes" answer for suicidal ideation, suicidal behavior, or self-injurious behavior without suicidal intent.

